#### **8.4.3.1. Back-up system in case the electronic reporting system does not work**

If the electronic reporting system does not work, the investigator (or designate) must complete, then date and sign a paper Expedited Adverse Events Report and fax it to the Study Contact for Reporting SAEs (refer to the [Sponsor Information](#)) or to GSK Biologicals Clinical Safety and Pharmacovigilance department within 24 hours.

This back-up system should only be used if the electronic reporting system is not working and NOT if the system is slow. As soon as the electronic reporting system is working again, the investigator (or designate) must complete the electronic Expedited Adverse Events Report within 24 hours. The final valid information for regulatory reporting will be the information reported through the electronic SAE reporting system.

#### **8.4.4. Updating of SAE information after removal of write access to the subject's eCRF**

When additional SAE information is received after removal of the write access to the subject's eCRF, new or updated information should be recorded on the appropriate paper report, with all changes signed and dated by the investigator. The updated report should be faxed to the Study Contact for Reporting SAEs (refer to the [Sponsor Information](#)) or to GSK Biologicals Clinical Safety and Pharmacovigilance department within the designated reporting time frames specified in [Table 15](#).

#### **8.4.5. Regulatory reporting requirements for serious adverse events**

The investigator will promptly report all SAEs to GSK in accordance with the procedures detailed in Section [8.4.1](#). GSK Biologicals has a legal responsibility to promptly notify, as appropriate, both the local regulatory authority and other regulatory agencies about the safety of a product under clinical investigation. Prompt notification of SAEs by the investigator to the Study Contact for Reporting SAEs is essential so that legal obligations and ethical responsibilities towards the safety of other subjects are met.

Investigator safety reports are prepared according to the current GSK policy and are forwarded to investigators as necessary. An investigator safety report is prepared for a SAE(s) that is both attributable to the investigational vaccines and unexpected. The purpose of the report is to fulfil specific regulatory and GCP requirements, regarding the product under investigation.

## **8.5. Follow-up of adverse events and serious adverse events**

### **8.5.1. Follow-up of adverse events and serious adverse events**

#### **8.5.1.1. Follow-up during the study**

After the initial AE/SAE report, the investigator is required to proactively follow each subject and provide additional relevant information on the subject's condition to GSK Biologicals (within 24 hours for SAEs; refer to [Table 15](#)).

All SAEs documented at a previous visit/contact and designated as not recovered/not resolved or recovering/resolving will be reviewed at subsequent visits/contacts until the end of the study.

All AEs documented at a previous visit/contact and designated as not recovered/not resolved or recovering/resolving will be reviewed at subsequent visits/contacts until 31 days after the last vaccination.

#### **8.5.1.2. Follow-up after the subject is discharged from the study**

The investigator will follow subjects:

- with SAEs, or subjects withdrawn from the study as a result of an AE, until the event has resolved, subsided, stabilised, disappeared, or until the event is otherwise explained, or the subject is lost to follow-up.

If the investigator receives additional relevant information on a previously reported SAE, he/she will provide this information to GSK Biologicals using an electronic Expedited Adverse Events Report as applicable.

GSK Biologicals may request that the investigator performs or arranges the conduct of additional clinical examinations/tests and/or evaluations to elucidate as fully as possible the nature and/or causality of the AE or SAE. The investigator is obliged to assist. If a subject dies during participation in the study or during a recognised follow-up period, GSK Biologicals will be provided with any available post-mortem findings, including histopathology.

## **8.6. Treatment of adverse events**

Treatment of any AE is at the sole discretion of the investigator and according to current good medical practice. Any medication administered for the treatment of an AE should be recorded in the subject's eCRF (refer to [Section 6.7](#)).

## **8.7. Unblinding**

GSK Biologicals' policy (which incorporates ICH E2A guidance, EU Clinical Trial Directive and US Federal Regulations) is to unblind the report of any SAE which is unexpected and attributable/suspected to be attributable to the investigational vaccines, prior to regulatory reporting. The GSK Biologicals' Central Safety Physician is responsible for unblinding the treatment assignment in accordance with the specified timeframes for expedited reporting of SAEs (refer to Section 8.4.1).

## **9. SUBJECT COMPLETION AND WITHDRAWAL**

### **9.1. Subject completion**

A subject who is available for the concluding contact foreseen in the protocol is considered to have completed the study.

### **9.2. Subject withdrawal**

Withdrawals will not be replaced.

#### **9.2.1. Subject withdrawal from the study**

From an analysis perspective, a ‘withdrawal’ from the study refers to any subject who was not available for the concluding contact foreseen in the protocol.

All data collected until the date of withdrawal/last contact of the subject will be used for the analysis.

A subject is considered a ‘withdrawal’ from the study when no study procedure has occurred, no follow-up has been performed and no further information has been collected for this subject from the date of withdrawal/last contact.

Investigators will make an attempt to contact those subjects who do not return for scheduled visits or follow-up.

Information relative to the withdrawal will be documented in the eCRF. The investigator will document whether the decision to withdraw a subject from the study was made by the subject’s parent(s)/LAR(s), or by the investigator, as well as which of the following possible reasons was responsible for withdrawal:

- Serious adverse event.
- Non-serious adverse event.
- Protocol violation (specify).
- Consent withdrawal, not due to an adverse event\*.
- Moved from the study area.
- Lost to follow-up.
- Other (specify).

\*In case a subject is withdrawn from the study because the subject’s parent(s)/LAR(s) has withdrawn consent, the investigator will document the reason for withdrawal of consent, if specified by the subject’s parent(s)/LAR(s), in the eCRF.

Subjects who are withdrawn from the study because of SAEs/AEs must be clearly distinguished from subjects who are withdrawn for other reasons. Investigators will follow subjects who are withdrawn from the study as result of a SAE/AE until resolution of the event (see Section [8.5.1.2](#)).

### 9.2.2. Subject withdrawal from investigational vaccines

A 'withdrawal' from the investigational vaccines refers to any subject who does not receive the complete treatment, i.e., when no further planned dose is administered from the date of withdrawal. A subject withdrawn from the investigational vaccines may not necessarily be withdrawn from the study as further study procedures or follow-up may be performed (safety or immunogenicity) if planned in the study protocol.

Information relative to premature discontinuation of the investigational vaccines will be documented on the Vaccine Administration screen of the eCRF. The investigator will document whether the decision to discontinue further vaccination was made by the subject's parent(s)/LAR(s), or by the investigator, as well as which of the following possible reasons was responsible for withdrawal:

- Serious adverse event.
- Non-serious adverse event.
- Other (specify).

## 10. STATISTICAL METHODS

### 10.1. Primary endpoints

- Evaluation of immunogenicity in terms of anti-RV antibody concentrations.
  - Serum anti-RV IgA antibody concentrations expressed as GMCs 1-2 months after Dose 2 in each of the HRV liquid formulation groups (Liq\_A, Liq\_B and Liq\_C).
  - Anti-RV IgA antibody seroconversion rate\* 1-2 months after Dose 2 in the lyophilised and pooled liquid groups.
  - Serum anti-RV IgA antibody concentrations expressed as GMCs 1-2 months after Dose 2 in the lyophilised and pooled liquid groups.

\*Seroconversion rate is defined as the percentage of subjects who were initially seronegative (i.e., with anti-RV IgA antibody concentration < 20 U/mL prior the first dose of HRV vaccine) and developed anti-RV IgA antibody concentration  $\geq$  20 U/mL at Visit 3.

## 10.2. Secondary endpoints

- Solicited adverse events
  - Occurrence of each general solicited symptom within the 8 days (Day 0-Day 7) follow-up period after each dose of the lyophilised and PCV-free HRV liquid vaccine
- Unsolicited adverse events.
  - Occurrence of unsolicited AEs within 31 days (Day 0-Day 30) after any dose of HRV vaccine, according to the Medical Dictionary for Regulatory Activities (MedDRA) classification.
- Serious adverse events
  - Occurrence of serious adverse events from Dose 1 up to study end.
- Evaluation of immunogenicity in terms of anti-RV antibody concentrations.
  - Serum anti-RV IgA antibody concentrations  $\geq 90$  U/mL 1-2 months after Dose 2 in the lyophilised and pooled liquid groups.

[figure not shown]
## 10.3. Determination of sample size

The target enrolment will be 1600 subjects (400 subjects in each of the PCV-free liquid vaccine groups and 400 subjects in the lyophilised vaccine group) to obtain at least 1280 evaluable subjects (320 subjects in each of the PCV-free liquid vaccine groups and 320 subjects in the lyophilised vaccine group) for the evaluation of the co-primary objectives assuming that approximately 20% of the enrolled subjects will not be evaluable.

### 10.3.1. Control on type I error

A 2.5% nominal type I error will be used for each co-primary evaluation. To control the overall type I error below 2.5%, a hierarchical procedure will be used for the multiple study objectives as shown in [Figure 1](#).

**Figure 1 Sequence for evaluating the study objectives in order to control the overall type I error below 2.5%**

The sample size has been estimated in order to obtain at least 91% power to demonstrate the co-primary objectives. The power associated with the target sample size for the conclusion on each inferential objective of this study is detailed in Section 10.3.3.

**10.3.2. References for sample size**

**Table 16 Seroconversion rates and standard deviation for log10 transformed concentration post vaccination.**

Antigen	Endpoint	Rota-060 (Sep-ad group)	Rota-061 (Pooled Liq group)	Rota-061 (Lyo group)	Rota-036 (HRV group)	Rota-054 (HRV group)	Rota-023 (HRV group)	Rota-068 (HRV group)	Rota-028/029/030 (HRV group)
RV IgA	N	121	746	252	787	147	393	318	115
	SCR (>=20U/ml)	86.0%[95% CI: 78.5;91.6] *	88.6%[95%CI :86.1;90.8]	90.5% [95%CI: 86.2;93.8]	86.5%[95 %CI: 83.9;88.8]	85.7%[95% CI: 79.0;90.9]	76.8%[95% CI: 72.4;80.9]	88.1%[95 %CI: 84.0;91.4]	93.9%[95 %CI: 87.9;97.5]
	SD	0.728	0.791	0.791	0.735	0.747	0.760	0.710	0.625

SCR = Seroconversion rate

SD = Standard deviation for log10 transformed concentration post vaccination.

\*Seropositivity

### 10.3.3. Power computation

The power computations were based on the following methods

- Consistency on GMC: Type II error was obtained using Power Analysis and Sample Size (PASS) 2005, one-sided non-inferiority test for 2 means, under the alternative of equal means & alpha=2.5%. The type II error was multiplied by 6 to account for the 6 pair wise lot comparisons.
- NI on Seroconversion rate: Type II error was obtained using PASS 2005, one-sided non-inferiority test for 2 proportions, under the alternative of equal proportions (Miettinen and Nurminen’s Likelihood Score Test of the Difference).
- NI on GMC: Type II error was obtained using PASS 2005, one-sided non-inferiority test for 2 means, under the alternative of equal means and variances.

To account for the multiplicity of comparison, the global type II errors were conservatively estimated as the sum of individual type II errors.

**Table 17 Power to demonstrate that the two-sided 95% CIs on the anti-RV IgA GMC ratio between PCV free liquid vaccine, 1-2 months after dose 2 of HRV vaccine lots are within the [0.5; 2.0] interval for all the pair wise comparisons**

Endpoint	Standard deviation [Log 10 (titre)]	N evaluable (each PCV free HRV liquid group)	Power
Anti-RV IgA antibody concentration	0.750	320	99.4%
	0.790*	320	98.2%
	0.850	320	96.4%

\*=Reference used for the global power computation

**Table 18 Probability that the lower limit of 95% CI for the difference in seroconversion rate (the pooled PCV free liquid vaccine group minus the lyophilised vaccine group), 1-2 months after dose 2 of HRV vaccine is ≥-10%**

Seroconversion rate		N evaluable (pooled PCV free HRV liquid group)	N evaluable (lyophilised HRV group)	Power
Lyophilised formulation of HRV vaccine	Liquid formulation of PCV free HRV vaccine			
75%	75%	960	320	96.0%
80%	80%	960	320	98.1%
85%*	85%*	960	320	99.5%
90%	90%	960	320	99.9%

\*=Reference used for the global power computation

**Table 19 Probability that the lower limit of the 95% CI on anti-rotavirus IgA antibody GMC ratio (the pooled PCV free liquid vaccine group divided by the lyophilised vaccine group), 1-2 months after dose 2 of HRV vaccine is  $\geq 0.67$**

Endpoint	Standard deviation [Log 10 (titre)]	N evaluable (pooled PCV free HRV liquid group)	N evaluable (lyophilised HRV group)	Power
Anti-RV IgA antibody concentration	0.750	960	320	95.3%
	0.790*	960	320	93.2%
	0.850	960	320	89.4%

\*=Reference used for the global power computation

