## 2. OBJECTIVES

### 2.1. Co-Primary objectives

- To demonstrate the lot-to-lot consistency of the PCV-free liquid HRV vaccine in terms of immunogenicity as measured by serum anti-RV IgA antibody concentrations 1-2 months after Dose 2.

*Consistency will be demonstrated if, for all pairs of lots, the two-sided 95% confidence intervals (CIs) for the ratio of anti-RV IgA antibody GMCs 1-2 months after Dose 2 are within the [0.5; 2] clinical limit interval.*

- To demonstrate the immunological non-inferiority of PCV-free liquid HRV vaccine as compared to the currently licensed lyophilised HRV vaccine in terms of seroconversion rates 1-2 months after Dose 2.

*Non-inferiority will be demonstrated if the lower limit of the two-sided asymptotic standardized 95% CI for the difference in seroconversion rate between the PCV-free liquid HRV vaccine (pooled HRV liquid groups) and licensed lyophilised HRV vaccine is greater than or equal to -10%.*

- To demonstrate the non-inferiority of the PCV-free liquid HRV vaccine to that of the currently licensed lyophilised HRV vaccine in terms of serum anti-RV IgA antibody concentrations 1-2 months after Dose 2.

*Non-inferiority will be demonstrated if the lower limit of the two-sided 95% CI for the ratio of anti-RV IgA antibody GMCs 1-2 months after Dose 2 between the PCV-free liquid HRV vaccine (pooled HRV liquid groups) and the lyophilised HRV vaccine is greater than or equal to 0.67.*

Refer to Section 10.1 for the definition of the primary endpoints.

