### 11.1.7. Data presentation description

The following decimal description from the decision rules will be used for the demography, immunogenicity and safety/reactogenicity.

Display Table	Parameters	Number of decimal digits
All summaries	% of count, including LL & UL of CI	1
Demographic characteristics	Mean, median, SD	1
Immunogenicity	% of difference, including LL & UL of CI	2
Immunogenicity	GMC group ratio, including LL & UL of CI	2
Immunogenicity	Anti-RV IgA GMC	1

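### Table 19 is titled for a GMC-ratio limit of 0.67, but its printed powers fit 2/3; at 0.67 the power of GMC non-inferiority is 0.5 to 0.8 points lower

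*Protocol*

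**What the plan says.** Protocol Section 2.1 declares GMC non-inferiority when the lower 95% limit of the ratio of pooled liquid "and the lyophilised HRV vaccine is greater than or equal to 0.67". SAP Section 3.1 repeats that limit, and the title of Protocol Table 19, which begins "Probability that the lower limit of the 95% CI on anti-rotavirus IgA antibody GMC ratio", carries it too.

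Section 10.3.3 describes the Table 19 calculation as a "one-sided non-inferiority test for 2 means, under the alternative of equal means and variances". Section 10.3.1 sets the error rate: "A 2.5% nominal type I error will be used for each co-primary evaluation". Table 19 uses 960 and 320 evaluable subjects and prints 95.3%, 93.2% (reference row) and 89.4% for standard deviations of 0.750, 0.790 and 0.850.

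For lot consistency (Table 17), "The type II error was multiplied by 6 to account for the 6 pair wise lot comparisons"; the printed powers are 99.4%, 98.2% (reference row) and 96.4%. Across objectives, "the global type II errors were conservatively estimated as the sum of individual type II errors". Below Figure 1 in Section 10.3.1 the protocol says: "The sample size has been estimated in order to obtain at least 91% power to demonstrate the co-primary objectives".

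**The concern.** Table 19 names its limit, method, group sizes and standard deviations, so its three powers can be recomputed exactly. They do not come out at 0.67. All three differ in the same direction, and the gap widens with the standard deviation, as it would if a slightly more lenient limit had been used.

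GMC non-inferiority has the lowest power of the three co-primary objectives, so it largely sets the overall power. A colleague who recomputes Table 19 at the limit that will be applied gets lower figures than those printed, and may wonder which limit the trial was planned on. The stake is an accurate record of planned power. Planning powers do not enter any analysis.

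**Working it through.** **Inputs.** One-sided 2.5% and true GMC ratio 1 with equal variances (Sections 10.3.1 and 10.3.3); 960 and 320 evaluable subjects and log10 standard deviations of 0.750, 0.790 and 0.850 (Table 19); limit 0.67 (Section 2.1 and the Table 19 title).

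**Formula.** SE = SD × √(1/960 + 1/320). Noncentrality = −log10(limit) / SE. Power is the probability that a noncentral t on 1278 degrees of freedom exceeds its 97.5% critical value, 1.962.

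**Reference row, SD 0.790.** SE = 0.790 × 0.06455 = 0.05099.
- Limit 2/3: 0.17609 / 0.05099 = 3.453, power 93.20%. This is the printed 93.2%.
- Limit 0.67: 0.17393 / 0.05099 = 3.411, power 92.62%.

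**All rows.**

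| SD | Printed | Limit 2/3 | Limit 0.67 | Overstatement at 0.67 |
|---|---|---|---|---|
| 0.750 | 95.3% | 95.30% | 94.84% | 0.5 |
| 0.790 | 93.2% | 93.20% | 92.62% | 0.6 |
| 0.850 | 89.4% | 89.38% | 88.64% | 0.8 |

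**Other explanations tried.**
- Normal approximation instead of t: 94.87%, 92.66% and 88.69% at 0.67; 95.33%, 93.23% and 89.43% at 2/3. The conclusion is the same.
- Rounding the observed limit to two decimals before comparing it with 0.67 (SAP Section 11.1.7 shows "GMC group ratio, including LL & UL of CI" to two decimals). The lowest value displayed as 0.67 is 0.665, which gives 95.52%, 93.47% and 89.74%. No row matches.
- Working backwards, the limits that would print each power lie in 0.66628–0.66704, 0.66635–0.66694 and 0.66635–0.66681. All contain 2/3; none contains 0.67 or 0.665.

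**Table 17.** With 320 per lot, limit log10 2 = 0.30103 and power = 1 − 6β:

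| SD | Single-test power | 1 − 6β | Single-test power cut to 3 decimals | 1 − 6β after cutting | Printed |
|---|---|---|---|---|---|
| 0.750 | 0.99906 | 99.44% | 0.999 | 99.4% | 99.4% |
| 0.790 | 0.99783 | 98.70% | 0.997 | 98.2% | 98.2% |
| 0.850 | 0.99401 | 96.41% | 0.994 | 96.4% | 96.4% |

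The reference row is 98.7% without intermediate rounding. Truncating the single-test power before multiplying by 6 reproduces all three printed rows.

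**Overall power by the sum rule (reference rows, Table 18 as printed at 99.5%).**
- As printed: 100 − (1.8 + 0.5 + 6.8) = 90.9%; allowing for rounding of the cells, 90.75% to 91.05%.
- Tables 17 and 19 restated at 0.67: 100 − (1.30 + 0.50 + 7.38) = 90.82%.
- Same with 2/3: 100 − (1.30 + 0.50 + 6.80) = 91.40%.

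**Overall power directly.** Simulating lot consistency and GMC non-inferiority together at 0.67, SD 0.790 and equal true GMCs (4 million replicates) gives 91.53%. Deducting the whole 0.5% printed type II error for seroconversion leaves 91.53 − 0.50 = 91.03%.

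**The case against.** The strongest reply is that 0.67 is simply 2/3 to two decimals, so the planners and the title may mean the same margin. That is a plausible account of how the figures arose. It does not make them right for the criterion as written: objectives, table title and SAP all give 0.67, and 0.67 is slightly stricter than 2/3. It is also fair that the gap is small. Moving the standard deviation from 0.750 to 0.850 changes Table 19 by about 6 points, roughly ten times as much, and the protocol already shows that range.

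Two stronger readings are tempting, and neither is supported.

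- A reader might infer that Table 17's 98.2% comes from a wrong input. The documents do not show that. Truncation accounts for all three rows using the stated inputs. It is an inference, since the protocol states no such step. Table 18 is compatible with it: a normal-approximation check of the score test gives 96.05%, 98.18%, 99.55% and 99.98%, against printed values of 96.0%, 98.1%, 99.5% and 99.9%. The printed 98.2% errs on the conservative side.
- A reader might infer from 90.9% or 90.8% that the claim of at least 91% is false. The protocol itself calls the sum rule conservative, so it is a lower bound on power; the printed cells allow up to 91.05% after rounding; and direct joint power at 0.67 is about 91.0% or more.

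**Conclusion.** Table 19 is wrong as titled: its powers do not follow from a limit of 0.67 and are 0.5, 0.6 and 0.8 percentage points too high. In the reference row the type II error is 7.4%, not 6.8%. That the printed values do not follow from 0.67 is calculation; that 2/3 was used instead is inference, though it fits every row.

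The point is minor. The applied limit is unambiguous, and no margin, sample size, test or conclusion depends on the table. The 98.2% in Table 17 is a secondary matter of rounding.

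The overall power statement stands. The joint figure behind that rests on the reference standard deviation of 0.790, equal true GMCs and variances, 320 evaluable infants per group, and Table 18's reference power of 99.5%.

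**What to change.** Restate Table 19 at the applied limit as 94.8%, 92.6% and 88.6%. Leave the 0.67 margin, the sample size and the analysis as they are.

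Optionally, reprint Table 17's reference row as 98.7%; leaving 98.2% is acceptable because it is conservative. Table 18 needs no change.

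The overall power sentence in Section 10.3.1 need not change. If a global figure is quoted from the sum rule, restate both tables and give it as 90.8%, described as a conservative bound. With Table 17 left at 98.2%, the same sum would read 100 − (1.8 + 0.5 + 7.4) = 90.3%.

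The cost is a text correction confined to Section 10.3.3, plus one phrase wherever a sum-rule figure is quoted.

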## 10.4. Analyses Sets

Note that in order to align to ICH and Clinical Data Interchange Standards Consortium (CDISC) terminology the Total vaccinated cohort (TVC) and the According-To-Protocol (ATP) cohort used in previous Rota studies have been renamed as Exposed Set (ES) and PPS, respectively.

### 10.4.1. Exposed Set

The ES will include all subjects with at least one study vaccine administration documented:

- a safety analysis based on the ES will include all vaccinated subjects,
- an immunogenicity analysis based on the ES will include all vaccinated subjects for whom immunogenicity data are available.

The ES analysis will be performed per treatment actually administered at dose 1.

